4 RESEARCH QUESTION/AIM(S)

The purpose of the present study is to test whether theory and evidence-based alternative communication formats, targeting message specificity and previously identified psychosocial predictors of adherence, could improve the behavioural impact of existing alert systems, compared to the official messages sent in association with the UK AQIs.

Research questions

Primary questions:

1) What is the main effect of using behaviourally enhanced messages, compared to the currently used DAQI messages, to present the health advice associated with air quality notifications for a hypothetical high air pollution scenario on adherence intentions?

Prediction:

A) The behaviourally enhanced messages will lead to stronger intentions to adhere to recommendations.

2) What is the main effect of using a behaviourally enhanced message, compared to the currently used DAQI messages, to present the health advice associated with air quality notifications on actual behaviour changes at four weeks?

Prediction:

A) The enhanced messages will lead to greater behaviour changes.

3) In case of a real alert being issued during the study period, how do the different messages affect actual behaviour change?

Prediction:

A) The enhanced messages will lead to greater behaviour change.

Secondary questions:

4) If there is a format effect, which variables mediate the relationship between the information format and behaviour change?

5) Which factors are associated with greater behaviour change across all groups?

5. METHODS

5.1 DESIGN

This is a randomised control trial using a 2-way factorial design, with target population (2 levels: general population vs. individuals with a pre-existing health condition) and message format (2 levels: usual message format vs. behaviourally enhanced messages) as between-factors. Participants will be randomised to either the usual message group or the enhanced message.

[figure not shown]

Figure 2 Study flow diagram

5.2 STUDY SETTING

Participants will be able to complete the relevant questionnaires at home (Via the app on their own smart device)

5.3 SAMPLE

Inclusion criteria

Inclusion:

- Users of air alert systems managed by the ERG
- Age: > 18 years
- Working or living in Greater London.

Exclusion criteria

- younger than 18 years
- not working or living in Greater London
- no longer users of the air quality alert smartphone application.

Sampling

Sample size was calculated using the G*Power statistical power analysis (32), to give 80% power to detect a statistically significant difference in the main outcome measures at $\alpha=0.05$, if a small to medium effect size of $f=0.02$ or higher is observed (9), adjusting for one covariate. Given the possibility of dropout, we inflated the sample size by 20%, and aimed to achieve a minimum sample size of $n=240$.

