6. STATISTICAL ANALYSES

6.1 Quantitative data

ANCOVAs will be performed for all the intentions measures in relation to the high air pollution hypothetical scenario, adjusting for baseline measures collected about one month earlier (target population and intervention/control group entered as fixed factors). Both main and interaction effects will be tested. ANCOVAs will also be performed for the actual behaviour change at 4 weeks (with the intervention/control group entered as fixed factor). These latter analyses will also be ran in the subgroups of healthy and at-risk participants. Chi square tests will be performed to analyse differences in proportion of self-reported actual behaviour change between groups, in relation to a real moderate air pollution episode. A two-way MANOVA (1000 bootstraps) will test whether there are differences between groups (both main effects and interactions) in perceived susceptibility, worry, severity, perceived response efficacy, perception of time, self-efficacy, trust, clarity, credibility and perceived informed choice measures. Multiple linear regressions will be used to assess the associations between main predictor variables and self-reported behaviour change at 4 weeks. Mediations effects of predictor variables on significant behavioural changes will be tested using PROCESS macro (38).

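### The printed effect size f=0.02 is incompatible with 80% power and n=240: it would need about 19,600 analysable participants, whereas 240 fits f=0.20 for a 1-df effect

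*Combined protocol and SAP*

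**What the plan says.** Section 5.3 (Sampling) says that G*Power was used "to give 80% power to detect a statistically significant difference in the main outcome measures" at alpha 0.05, "if a small to medium effect size of $f=0.02$ or higher is observed (9), adjusting for one covariate". On dropout it continues that "we inflated the sample size by 20%, and aimed to achieve a minimum sample size of $n=240". It gives no numerator degrees of freedom, number of groups, pre-inflation N or expected dropout rate.

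Two other sections bear on the degrees of freedom. Section 5.1 describes a two-way factorial design with two levels of target population and "message format (2 levels: usual message format vs. behaviourally enhanced messages) as between-factors". Section 6.1 plans ANCOVAs of the intention measures adjusted for baseline, with "target population and intervention/control group entered as fixed factors", and tests main effects and the interaction. No other section restates or corrects the effect size.

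**The concern.** Cohen's f of 0.02 is a very small standardised effect, equivalent to d = 2f = 0.04 between two equal groups. A trial of a few hundred people cannot detect it with 80% power. The value also sits badly with the plan's own description of it as lying between small and medium.

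This paragraph is the only place that says what effect the trial is sized to detect. As printed, the sample size cannot be reproduced. A reader would also believe the trial is sensitive to an effect about one tenth of what it can detect, and could take a null result as ruling out very small effects.

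**Working it through.** **Inputs.** From section 5.3: alpha 0.05, power 80%, f=0.02, one covariate, 20% inflation, target 240. From sections 5.1 and 6.1: two factors with two levels each, so four cells, and 1 numerator df for each main effect and for the interaction. The 3-df case, a joint test of the four cells, is included because section 5.3 does not state the df.

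**Formula.** Power is P(F′ > F_crit), where F′ is noncentral F with noncentrality λ = f²N, numerator df 1 or 3, and error df = N − groups − 1 (the covariate costs one df). Taking two or four groups gives the same N for a 1-df effect.

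**Step 1: try to reproduce 240 from the printed inputs.** A 1-df test needs λ of about 7.85 for 80% power in a large sample.

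- Required N at f=0.02: 7.85 / 0.02² = 7.85 / 0.0004 = 19,625. The exact noncentral-F search also gives 19,625, and the normal approximation gives 19,624.
- After inflation: 19,625 × 1.2 = 23,550.
- With 3 df, 27,261 analysable are needed.
- At N=200, λ = 0.0004 × 200 = 0.08 and power is 5.9%. It is also 5.9% at N=192 and 6.1% at N=240.

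The stated figure is not reproduced. The ratio is 19,625 / 200 = 98.

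**Step 2: try other meanings of 0.02 and nearby settings.**

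| Reading | df | f | Analysable N for 80% | × 1.2 |
|---|---|---|---|---|
| As printed | 1 | 0.02 | 19,625 | 23,550 |
| 0.02 is f² | 1 | 0.141 | 395 | 474 |
| 0.02 is η² | 1 | 0.143 | 387 | 464 |
| Decimal moved | 1 | 0.20 | 199 | 239 |
| Decimal moved | 3 | 0.20 | 277 | 332 |
| Solved to give N=200 | 3 | 0.236 | 200 | 240 |

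Here η² converts as f = √(0.02/0.98) = 0.143. A one-sided-equivalent test (alpha 0.10) at f=0.02 still needs 15,457.

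**Step 3: could the covariate close the gap at f=0.02?** If the baseline measure cut the error variance by the factor 1 − r², N would fall by the same factor. To go from 19,625 to 200, r = √(1 − 200/19,625) = 0.995, which is not credible for a questionnaire repeated after a month.

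**Step 4: what the planned size delivers at f=0.20.**

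| Analysable N | Power, 1 df | Power, 3 df |
|---|---|---|
| 192 (20% of 240 lost) | 78.7% | 62.4% |
| 200 | 80.4% | 64.4% |
| 240 | 87.0% | 73.4% |

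With 1 df, the smallest f detectable at 80% power is 0.199 with 200 analysable and 0.203 with 192. The largest loss from 240 that still leaves 199 is 41/240 = 17.1%.

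**The case against.** The strongest counter-argument is that f=0.20 is not the only route to 240. Suppose 0.02 is f² on the unadjusted scale and the baseline covariate explains variance as well as costing a df. The effective f is then 0.141/√(1 − r²). Under assumed correlations, which the plan does not give, the required N is:

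| Assumed r | N | × 1.2 |
|---|---|---|
| 0.50 | 297 | 356 |
| 0.60 | 254 | 305 |
| 0.70 | 203 | 244 |
| 0.71 | 197 | 236 |

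So r of about 0.70 would also land near 240, and the unadjusted target would be f of about 0.14. This stands as a possibility, but it needs an unstated correlation, and the printed symbol and value would still be wrong.

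A second objection is that an adequate N for one ANCOVA effect is not adequate for everything planned. Section 4 lists three primary questions, and section 6.1 adds chi-square tests and ANCOVAs within the healthy and at-risk subgroups. That is fair: reassurance about 240 extends only to a 1-df ANCOVA effect of f=0.20 in the full sample.

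Third, on the likely reading nothing changes in recruitment, design or analysis, so the point could be graded as a reporting correction. The error is nonetheless certain, it is in the only sizing parameter, and until the df is confirmed the adequacy of 240 is not established.

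The ×1.2 inflation is not itself a fault. Dividing by 0.8 would give 249, but no dropout rate is stated, so inflating by a fifth is consistent with the text.

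**Conclusion.** The point holds, and section 5.3 is wrong as written. Under the printed inputs, the required number is 19,625 analysable participants (1 df) or 27,261 (3 df), and power with about 200 is 5.9% (1 df), not 80%. The effect detectable with about 200 analysable is roughly ten times the printed value: f of about 0.20 with 1 df, or about 0.236 with 3 df.

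The contradiction depends only on the plan's own figures and the standard ANCOVA power formula. The diagnosis, f=0.20 with 1 df, is an inference. It rests on the match 199 × 1.2 = 239, the plan's verbal description of the effect, and the two-level factors. If it is right, only the printed parameter is wrong and 240 is adequate for that effect in the full sample. If f=0.20 was meant for a 3-df test, power with 200 is 64% and 240 is too few.

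**What to change.** Check the saved G*Power output for the effect size, numerator df, number of groups and N, then correct section 5.3. Suggested text, with bracketed values to be confirmed:

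> Sample size was calculated in G*Power (ANCOVA, numerator df = [1], one covariate) to give 80% power at alpha = 0.05 to detect f = [0.20] for the [message-format main effect], which requires [199] analysable participants. This was inflated by 20% to a minimum of n = 240. With 240 recruited, 80% power at f = [0.20] is kept for a loss of up to about [17%]; with a 20% loss (192 completers) power is about [79%].

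If the output shows another f or df, or an assumed baseline correlation, print those values and the N that belongs to them.

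The cost is one look at the saved settings and one or two sentences. No extra participants are needed on the f=0.20, 1-df reading. If the output shows f=0.20 with 3 df, the target would need revisiting (277 analysable; 277 × 1.2 = 332).

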5.4 STUDY PROCEDURE

5.4.1 CityAir smartphone application

This is an application designed and developed by the City of London Corporation and King's College London. The CityAir app version 2.0.4 (available at: <https://www.cityoflondon.gov.uk/business/environmental-health/environmental-protection/air-quality/Pages/New-CityAir-App.aspx>) is currently available for iOS and Android and is compatible with iPhone, iPad and iPod touch and Android devices. This application allows users to sign up for air pollution alerts and find less polluted routes when levels of air pollution are high in London. In addition, it provides users with targeted advice for generally healthy and at risk individuals on how to reduce exposure to air pollution. Such advice is based on the official UK AQIs. The application also provides simple advice for users registered as cyclists, pedestrian, jogger, drivers, and businesses on how to reduce emissions and exposure (e.g. advice for drivers: 'Turn off your engine when parked'; for joggers: 'Consider delaying your jog till pollution levels are lower'; for businesses: 'Check out the CityAir guides to help lower pollution levels in the City').

For the purpose of the current study, KCL will launch an alternative version, which will allow the researchers to send different types of messages for the control and intervention groups during the study period. To increase message relevance, targeted advice will be sent to people with lung and/or heart or other existing condition, and the generally healthy public (see Table 3). It is worth noting that the current UK AQI does not provide targeted advice for people with heart conditions apart from reducing exertion, and the main advice for people with lung conditions is to consider using their reliever inhaler more often. Usually CityAir sends alerts for moderate, high and very high air pollution to users in the at-risk group, whilst sending only alerts for high and very high air pollution to users in the other groups. However, for the purpose of the current study, the alternative version of the application also will send moderate alerts and associated advice to the general population group. This will allow to actually test the UK AQI advice in case of a real moderate air pollution episode during the study period. To keep the study design simple, we will not differentiate between cyclists, joggers, and pedestrians. However, general messages also will include advice on how to adjust these types of physical activity to reduce exposure. Personal device IDs (i.e. an anonymous and unique identifier attributed to an individual mobile device) will be used to link

questionnaires completed at different time points by the same study participant. At the end of the study, a new version of CityAir will be issued to allow the application to go back to its usual functions.

5.4.2 Recruitment and study procedure

All CityAir application users will be sent a notification about the current study containing a link to the participant information sheet. If eligible and happy to take part in the study, then they will be redirected to an online survey, using a well-known online platform (<https://www.surveymonkey.co.uk/>).

Once potential participants had agreed to take part, they will be asked to indicate whether they had a pre-existing health condition. Based on their answers, they will be divided into two groups (general public and at risk respondents). Respondents in both groups will be randomised via an algorithm run by CityAir to either a control or intervention condition.

Participants will be asked to read the scenario of a hypothetical high pollution episode and to indicate their intentions to follow the health advice given (i.e. baseline adherence intentions measure). After completion of the first questionnaire, all participants will be able to receive real-time CityAir notifications about real air pollution episodes. Whilst the control group will receive air quality notification and associated health advice in the usual UK AQI format, the intervention group will receive health advice in an alternative format (see Materials).

5.5 MATERIALS:

Table 2 shows the health advice accompanying air quality alerts in both the usual and alternative format (i.e. targeting message specificity). Table 3 shows some of the additional messages that will be sent to the intervention group and targeting specific psychosocial factors identified in our previous systematic review. Readability scores were calculated for all messages (using a readability tool available at: <https://www.webpagefx.com/tools/read-able/check.php>) and reported in Tables 2-3. To reduce the likelihood of confounding effects, the alternative messages have a similar word count and identical readability scores of 8 (i.e. they should be easily understood by 13 to 14 years old).

SHORT TITLE/ACRONYM: Improving the health impact of air quality alerts v.3

Table 2 The health advice associated with the current UK AQI compared with the alternative/more detailed health messages developed for this study.

Level of pollution	Usual messages of UK AQI*		Alternative messages (targeting message specificity)	
	General public	At risk	General public	At risk
Moderate 4-6	Enjoy your activities as usual ^a	Adults and children with lung problems, and adults with heart problems, who experience symptoms, should consider reducing strenuous physical activity, particularly outdoors. ^b	
Enjoy your activities as usual. However, if you wanted you, you can reduce your exposure to pollution by reducing levels and length of physical activity outdoors.
 
You can also consider changing:
 
 • Travel route or • Exercise location (e.g. use our app to find less polluted roads or parks) or • Time (e.g. mornings or less polluted times). ^e 	
Adults and children with lung problems, adults with heart problems, and older people, should reduce levels and length of physical activity outdoors.
 
Where possible, change:
 
 • Travel route or • Exercise location (e.g. use our app to find less polluted roads or parks) or • Time (e.g. mornings or less polluted times). ^h
High 7-9	Anyone experiencing discomfort such as sore eyes, cough or sore throat should consider reducing activity, particularly outdoors. ^c	Adults and children with lung problems, and adults with heart problems, should reduce strenuous physical exertion, particularly outdoors, and particularly if they experience symptoms. People with asthma may find they need to use their reliever inhaler more often. Older people should also reduce physical exertion. ^d	
Anyone who experiences sore eyes, cough or sore throat should consider limiting their exposure to air pollutants.
 
To do this, you don't need to stay indoors, instead you can reduce levels and length of physical activity outdoors.
 
You can also consider changing:
 
 • Travel route or • Exercise location (e.g. use our app to find less polluted roads or parks) or 	
Adults and children with lung problems, adults with heart problems, and older people, should reduce levels and length of physical activity outdoors.
 
People with asthma may find they need to use their reliever inhaler more often.
 
Where possible, change:
 
 • Travel route or • Exercise location (e.g. use our app to find less polluted roads or parks) or

SHORT TITLE/ACRONYM: Improving the health impact of air quality alerts v.3

			
 • Time (e.g. mornings or less polluted times).ⁱ 	
 • Time (e.g. mornings or less polluted times).ⁱ
Very high 10	Reduce physical exertion, particularly outdoors, especially if you experience symptoms such as cough or sore throat. ^e	Adults and children with lung problems, adults with heart problems, and older people, should avoid strenuous physical activity. People with asthma may find they need to use their reliever inhaler more often. ^f	
Reduce levels and length of physical exertion, in particular outdoors, even more so if you experience symptoms such as cough or sore throat.
 
Where possible, change:
 
 • Travel route or • Exercise location (e.g. use our app to find less polluted roads or parks) 
or
 
 • Time (e.g. mornings or less polluted times).^l 	
Adults and children with lung problems, adults with heart problems, and older people, should avoid intense physical activity.
 
People with asthma may find they need to use their reliever inhaler more often.
 
Where possible, change:
 
 • Travel route or • Exercise location (e.g. use our app to find less polluted roads or parks) 
or
 
 • Time (e.g. mornings or less polluted times).ⁱ

Note: For each message word count and readability score are reported (i.e. higher scores indicate more complex sentences). a. Word count: 5, readability score: 12 (It should be easily understood by 17 to 18 year olds); b. Word count: 22, readability score: 20; c. Word count: 17, readability score: 18 (understood by 23 to 24 year olds); d. Word count: 45, readability score: 14 (understood by 19 to 20 year olds); e. Word count: 16, readability score: 16 (understood by 21 to 22 year olds); f. Word count: 32, readability score: 12; g. Word count: 53, readability score: 7 (understood by 12 to 13 years old); h. Word count: 49, readability score: 8 (understood by 13 to 14 years old); i. Word count: 62, readability score: 8; l. Word count: 50, readability score: 8. These messages were reviewed by both the ERG and PPI groups.

SHORT TITLE/ACRONYM: Improving the health impact of air quality alerts v.3

Table 3 A few examples of additional messages developed and aiming to target specific psychosocial factors.

Targeted Variable	General population	At risk - other	At risk: lung-specific	At risk: heart-specific	At-risk: combo
Response efficacy	Taking a side street route cuts a person's exposure to air pollution by half	Taking a side street route cuts a person's exposure to air pollution by half	Taking a side street route cuts a person's exposure to air pollution by half	Taking a side street route cuts a person's exposure to air pollution by half	Taking a side street route cuts a person's exposure to air pollution by half
			If you have a preventer inhaler, using it every day will reduce the inflammation that causes asthma. Your reliever inhaler will help to ease symptoms straight away.		If you have a preventer inhaler, using it every day will reduce the inflammation that causes asthma. Your reliever inhaler will help to ease symptoms straight away.
Response costs (i.e. negative consequences associated with the recommended behaviour)	The CityAir App can help you find side street routes, which do not necessarily add to your total travel time, and may give you a more pleasant journey.	The CityAir App can help you find side street routes, which do not necessarily add to your total travel time, and may give you a more pleasant journey.	The CityAir App can help you find side street routes, which do not necessarily add to your total travel time, and may give you a more pleasant journey.	The CityAir App can help you find side street routes, which do not necessarily add to your total travel time, and may give you a more pleasant journey.	The CityAir App can help you find side street routes, which do not necessarily add to your total travel time, and may give you a more pleasant journey.
	Before you go out walking, jogging or cycling check our App to find less polluted areas where exercising. Start by exploring green areas and parks close to your house or office.	Before you go out walking, jogging or cycling check our App to find less polluted areas where exercising. Start by exploring green areas and parks close to your house or office.	Before you go out walking, jogging or cycling check our App to find less polluted areas where exercising. Start by exploring green areas and parks close to your house or office.	Before you go out walking, jogging or cycling check our App to find less polluted areas where exercising. Start by exploring green areas and parks close to your house or office.	Before you go out walking, jogging or cycling check our App to find less polluted areas where exercising. Start by exploring green areas and parks close to your house or office.
			People with asthma may worry about using their preventer inhalers every day. However, you should know that these medications are safe to use daily. They should also reduce your need for the reliever inhaler		People with asthma may worry about using their preventer inhalers every day. However, you should know that these medications are safe to use daily. They should also reduce your need for the reliever inhaler

SHORT TITLE/ACRONYM: Improving the health impact of air quality alerts v.3

The table reports the specific variable targeted by the messages, and who is the target of the messages. Although the majority of messages targeting the at-risk group are identical, some are slightly adjusted depending on whether people had a pre-existing lung and/or heart disease, or if they report to be at risk for other conditions including old age. This is to make sure that participants are not receiving messages irrelevant to them, as this may lead to confusion, loss of interest, and mistrust (e.g. (33)). The average readability scores were 9.3 (i.e. easily understood by 14 to 15 year olds) and 9.8 (i.e. easily understood by 15 to 16 year olds), for the general population and at-risk groups (all messages considered) respectively. These messages were reviewed by both the ERG and PPI groups.

